### Peripheral Neuropathy

Any event suspected or diagnosed as Peripheral Neuropathy would be considered as an AESI. For the treatment interruption rules, please see [Section 3.3.4.3](#) Implications of specific adverse events.

#### 5.2.6.1.5 Intensity (severity) of AEs

The intensity grading of AEs will be performed according to Rheumatology Common Toxicity Criteria (RCTC) Version 2.0 developed by [REDACTED] [\[R13-3515\]](#). Refer to the ISF for intensity/severity classification. Intensity options are:

Grade 1	mild
Grade 2	moderate
Grade 3	severe
Grade 4	includes life-threatening

#### 5.2.6.1.6 Causal relationship of AEs

Medical judgement should be used to determine whether there is a reasonable possibility of a causal relationship between the adverse event and the given study treatment, considering all relevant factors, including pattern of reaction, temporal relationship, de-challenge or re-challenge, confounding factors such as concomitant medication, concomitant diseases and relevant history.

Arguments that may suggest that there is a reasonable possibility of a causal relationship could be:

- The event is consistent with the known pharmacology of the drug.
- The event is known to be caused by or attributed to the drug class.
- A plausible time to onset of the event relative to the time of drug exposure.
- Evidence that the event is reproducible when the drug is re-introduced.

- No medically sound alternative aetiologies that could explain the event (e.g. pre-existing or concomitant diseases, or co-medications).
- The event is typically drug-related and infrequent in the general population not exposed to drugs (e.g. Stevens-Johnson syndrome).
- An indication of dose-response (i.e. greater effect size if the dose is increased, smaller effect size if dose is reduced).

Arguments that may suggest that there is no reasonable possibility of a causal relationship could be:

- No plausible time to onset of the event relative to the time of drug exposure is evident (e.g. pre-treatment cases, diagnosis of cancer or chronic disease within days / weeks of drug administration; an allergic reaction weeks after discontinuation of the drug concerned).
- Continuation of the event despite the withdrawal of the medication, taking into account the pharmacological properties of the compound (e.g. after 5 half-lives).
- Of note, this criterion may not be applicable to events whose time course is prolonged despite removing the original trigger.
- Additional arguments amongst those stated before, like alternative explanation (e.g. situations where other drugs or underlying diseases appear to provide a more likely explanation for the observed event than the drug concerned).
- Disappearance of the event even though the trial drug treatment continues or remains unchanged.

#### 5.2.6.2 Adverse event collection and reporting

##### 5.2.6.2.1 AE Collection

The investigator shall maintain and keep detailed records of all AEs in the patient files. The following must be collected and documented on the appropriate CRF(s) by the Investigator (special notes on SAE form reporting where needed):

- From the time of first dose of trial drug administration in the extension trial until the EoS-visit:

all AEs (serious and non-serious) and all AESIs

- All AEs that started in the parent trial (onset date in parent trial) and are still ongoing after 1st IMP administration in the extension trial:
  - Re-record the AE in the extension trial eCRF with the same information as it was recorded in the parent trial.
  - Should the AE end during the course of the extension trial (after 1st IMP administration in the extension trial), update only the extension trial eCRF; However, concerning reporting on the SAE form (if applicable), the follow-up report will still be sent on the parent trial SAE form, no new SAE form is to be completed for the extension trial.

- If the intensity of an ongoing AE changes after 1st IMP administration in the extension trial:
  - ⇒ update only the extension trial eCRF;
    - The AE with the new intensity will be handled as new event with the onset of the new intensity as start date; Example: If the intensity increased then the new AE name/term should contain “Worsening of...” or “Exacerbation of...”.

Considerations for reporting on the SAE form, when intensity change qualifies as worsening/exacerbation of an event that had already been reported on the SAE form:

- corresponding follow up report to be sent on the parent trial SAE form with date of worsening as event end date.
- extension trial SAE form to be sent as initial report for the extension trial for new event “worsening/exacerbation of...” with date of worsening as onset date.

Considerations for reporting on the SAE form, when intensity change qualifies as worsening/exacerbation of an event and requires for the first time reporting on the SAE form (meeting for the first time seriousness/AESI criteria):

- only extension trial SAE form to be sent - as initial report for the extension trial for new event “worsening/exacerbation of...” with date of worsening as onset date.

- All AEs with an end date **before** the 1st IMP administration in the extension trial, even if Informed Consent of the extension trial was already signed:
  - Record only in the eCRF of the parent trial.
  - In case of an AE reportable on the SAE form, send the update only on the SAE form of the parent trial.
  - Do not re-record in the extension trial eCRF, do not complete a new SAE form for the extension trial.

After the EoS visit in the extension trial:

After a patient’s EoS-visit in the extension trial the investigator does not need to actively monitor the patient for new AEs but should only report new malignancies or the exacerbation of existing malignancies, trial treatment related SAEs and trial treatment related AESIs of which the investigator may become aware of by any means of communication, e.g. phone call. Those AEs should be reported on the BI SAE form (see [Section 5.2.6.2.2](#)) for the extension trial, but not on the CRF (neither on CRF for extension nor for parent trial).

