#### 2.1.2 Primary endpoint(s)

The primary endpoint is the occurrence of treatment emergent adverse events (TEAEs) up to week 260 of maintenance treatment.

Note: TEAEs are defined as all adverse events occurring between start of treatment in the extension trial and the end of its residual effect period. Adverse events that start before first drug intake in the extension trial and deteriorate under treatment during the extension trial will also be considered as 'treatment-emergent'.

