### 7.2.5 Safety analyses

Adverse events will be coded using the Medical Dictionary for Drug Regulatory Activities (MedDRA). Standard BI summary tables and listings will be produced. All adverse events with an onset between start of treatment and end of the REP, a period of 16 weeks after the last dose of study medication, will be assigned to the on-treatment period for evaluation.

All treated patients will be included in the safety analysis. In general, safety analyses will be descriptive in nature and will be based on BI standards. No hypothesis testing is planned.

Statistical analysis and reporting of adverse events will concentrate on treatment-emergent adverse events, i.e. all adverse events occurring between start of treatment and end of the REP. Adverse events that start before first drug intake and deteriorate under treatment will also be considered as 'treatment-emergent'.

Frequency, severity, and causal relationship of all treatment emergent adverse events will be tabulated by system organ class and preferred term after coding according to the current version of the Medical Dictionary for Drug Regulatory Activities (MedDRA) at database lock. Exposure adjusted incidence rate of all treatment emergent adverse events will also be presented.

The exposure adjusted incidence rate (per 100 subject years) of a selected treatment emergent adverse event is defined as the number of subjects experiencing the adverse event per treatment group during time at risk divided by the total time of subjects at risk in that treatment group to contribute the event to the analysis multiplied by 100 (per 100 subject year), where:

$$\text{Time at risk [subject years]} = (\text{date of onset of TEAE} - \text{study drug start date} + 1) / 365.25$$

If, for a subject, the selected treatment emergent adverse event didn't occur then the time at risk will be censored at min (date of death, last contact date per EoS page, drug stop date +

112 days). For each selected treatment emergent AE, the exposure adjusted incidence rate will be calculated as:

$$\text{Incidence rate [1/100 Subject years (pt-yrs)]} = 100 * \text{number of subjects with TEAE} / \text{Total TEAE-specific time at risk [subject years]}.$$

Laboratory data will be analysed both quantitatively as well as qualitatively. The latter will be done via comparison of laboratory data to their reference ranges. Values outside the reference range as well as values defined as clinically relevant will be summarised.

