6. GENERAL ANALYSIS DEFINITIONS

6.1 TREATMENT(S)

The following maintenance treatment is planned in this study:

Spesolimab 600 mg q4w s.c. for up to 5 years for patients who have completed and clinically responded to the treatment with study drug (Spesolimab) in previous trials.

The following study phases are defined:

Table 6.1: 1 Flow chart of analysis phases of the study

Study analysis phase	Description	Start (included)	End (included)
Screening phase	Screening	Earliest of i) Date of informed consent, ii) First screening procedure	Date/time of start of injection for maintenance study drug minus 1 second
Maintenance treatment phase & Residual effect period	Maintenance on-treatment period	Date/time of start of injection of first maintenance study drug (Day 1 for maintenance)	Earliest of: i) Date of injection of last maintenance study drug + 112 days at 23:59, ii) cut-off for interim analysis if applicable.
Follow-up ¹ phase	Off-treatment period	Date of injection of last maintenance study drug + 113 days at 12:00 a.m.	Latest of: i) Date of EOS visit (Week 276 visit); ii) Last contact date on End of Study page at 11:59 p.m.

Dates are defined individually per patient. If more than one date is associated with a specific visit, measurements associated with a specific date are assigned to a study analysis phase according to the rules specified in the table. An analysis phase will not extend beyond the start date of the following phase.

¹ The follow-up phase only exists if the date of EOS visit or the last contact date is after the date of injection/infusion of last study drug + 112 days.

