7.8.1 Adverse Events

AEs will be coded with the most recent version of MedDRA.

The analyses of AEs will be descriptive in nature. All analyses of AEs will be based on the number of patients with AEs and not on the number of AEs. System organ classes (if applicable) will be sorted according to the standard sort order specified by the EMA, preferred terms (if applicable) will be sorted by total frequency (within system organ class).

For details on summarization of AE data, please refer to "Analysis and Presentation of Adverse Event data from Clinical Trials" ([6](#)), "Analysis and Presentation of Adverse Event data from Clinical Trials – Display Template" ([7](#)) and "Handling of missing and incomplete AE dates" ([4](#)).

The analysis of AEs will be based on the concept of treatment emergent AEs. This means that all AEs will be assigned to the screening period, maintenance period (i.e. maintenance treatment phase plus REP) or off-treatment period (i.e. follow up) as defined in [Section 6.1](#). Since only the start date of an AE is collected (without start time), any AE occurrence on the same day as the first Spesolimab administration will be assigned to the on-treatment phase.

Exposure-adjusted adverse event incidence rates for TEAE will be calculated using the following approach:

- 1) The exposure adjusted incidence rate (per 100 subject years) of a selected treatment emergent adverse event is defined as the number of subjects experiencing the adverse event per treatment group during time at risk divided by the total time of subjects at risk to contribute the event to the analysis multiplied by 100 (per 100 subject years), where:

$$\text{Time at risk [subject years]} = (\text{date of onset of AE} - \text{first treatment start date} + 1) / 365.25$$

- 2) If, for a subject, the selected treatment emergent adverse event didn't occur, then the time at risk will be censored at min (date of death, last contact date per EoS page, cut-off date for the interim analysis, or the end of on-treatment period). For each selected treatment emergent AE, the exposure adjusted incidence rate will be calculated as:

$$\text{Incidence rate [1/100 Subject years (pt-yrs)]} = 100 * \text{number of subjects with TEAE} / \text{Total TEAE-specific time at risk [subject years]}.$$

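### An adverse event carried over from the parent trial that improves is recorded as a new on-treatment event, and nothing in the visible documents keeps it out of the TEAE count

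*Protocol*

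**What the plan says.** **Recording.** An AE that began in the parent trial and is still present after the first extension dose is entered again: "Re-record the AE in the extension trial eCRF with the same information as it was recorded in the parent trial" (Protocol 5.2.6.2.1). The same section then sets a rule that begins "If the intensity of an ongoing AE changes after" the first extension dose, and continues: "The AE with the new intensity will be handled as new event with the onset of the new intensity as start date". The trigger is a change in either direction. The naming example and the SAE-form instructions that follow deal with worsening only.

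**Classification.** Protocol 7.2.5 assigns to the on-treatment period "All adverse events with an onset between start of treatment and end of the REP", the REP being 16 weeks after the last dose. Protocol 2.1.2 and 7.2.5 add a second route into the TEAE definition: "Adverse events that start before first drug intake in the extension trial and deteriorate under treatment during the extension trial will also be considered" treatment-emergent. SAP Table 6.1: 1 starts the on-treatment period at the first extension injection and ends it 112 days after the last one, or at an interim cut-off if earlier. SAP 7.8.1 describes the allocation thus: "This means that all AEs will be assigned to the screening period, maintenance period (i.e. maintenance treatment phase plus REP) or off-treatment period". It does not repeat the deterioration clause and has no rule for a decrease in intensity.

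**Counting.** SAP 7.8.1 states: "All analyses of AEs will be based on the number of patients with AEs and not on the number of AEs". In the exposure-adjusted rate, a patient's time at risk for a term ends at the onset of the event.

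**The concern.** Everyone in this trial comes from a parent trial, so carried-over AEs are built into the design. Followed step by step, the text treats three patients with the same pre-existing AE in an odd way. The one whose AE persists unchanged has no TEAE. The one whose AE worsens has a TEAE, as intended. The one whose AE partly recovers also has a TEAE, dated at the recovery.

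TEAE occurrence is the primary endpoint. What is at stake is upward bias in preferred-term frequencies and exposure-adjusted rates, with a partial recovery shown as a new on-treatment event. One output also has a cut-off: SAP 7.8.1 lists, for registry disclosure, non-serious preferred terms with an incidence above 5%.

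**Working it through.** The documents give no figure on this point, so there is none to reproduce. The check has three parts.

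**1. Apply the definition to three carried-over AEs.** Example dates (assumed): parent-trial onset at Day -40, change of intensity at Day 57.

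| Carried-over AE | Start date of record | Date rule met? | Deterioration clause met? | TEAE? |
|---|---|---|---|---|
| Unchanged | Day -40 | no | no | no |
| Worsens | Day 57 | yes | yes | yes |
| Improves | Day 57 | yes | no | yes |

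The two routes are alternatives, so meeting either is enough. They differ only in the last row.

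**2. Effect of one patient on a frequency.** Input: about 500 patients expected (Protocol 7.5).

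- One patient: 1/500 = 0.2 percentage points.
- Relative to a term with 5, 25 or 50 true patients: 1/5 = 20%, 1/25 = 4%, 1/50 = 2%.
- At the disclosure cut-off: 25/500 = 5.0% (not above 5%); 26/500 = 5.2% (above).

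**3. Effect on the exposure-adjusted rate.** Formula (Protocol 7.2.5, SAP 7.8.1): 100 x patients with the TEAE / total time at risk in years. Document inputs: last dose at Day 1821, censoring 112 days later, so 1821 + 112 = 1933 days, and 1933/365.25 = 5.292 years. Assumptions: all 500 complete; 25 have a genuine event, on average at mid-follow-up (2.646 years); improvement-only records are dated Day 57 (57/365.25 = 0.156 years).

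- None counted: time = 25 x 2.646 + 475 x 5.292 = 2,580.0; rate = 2,500/2,580.0 = 0.97 per 100 patient-years.
- One counted: time = 25 x 2.646 + 0.156 + 474 x 5.292 = 2,574.8; rate = 2,600/2,574.8 = 1.01 (+4.2%).
- Five counted: time = 25 x 2.646 + 5 x 0.156 + 470 x 5.292 = 2,554.3; rate = 3,000/2,554.3 = 1.17 (+21%).

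The one-patient effect hardly depends on follow-up. With an assumed mean time at risk of 3 years and a false onset at 0.25 years, 26/(1,500 - 2.75) against 25/1,500 is 1.737 against 1.667 per 100 patient-years, again +4.2%.

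**How many such patients?** The documents do not say. For scale only, multiply 500 by four assumed shares: carry-over of the term, grade 2 or higher, step-down without resolution, and no other on-treatment event of that term.

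- Low: 500 x 0.005 x 0.10 x 0.25 x 0.7 = 0.04 patients per term.
- Middle: 500 x 0.01 x 0.25 x 0.4 x 0.8 = 0.4.
- High: 500 x 0.02 x 0.4 x 0.5 x 0.9 = 1.8.

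On these guesses, five patients in one term would be unusual.

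**The case against.** **A reader might infer that the documents contradict each other**, with the date rule counting an improvement and the deterioration clause excluding it. They do not. The clause says such AEs "Adverse events that start before first drug intake in the extension trial and deteriorate under treatment during the extension trial will also be considered" treatment-emergent: it adds cases and excludes none, and it concerns records that start before the first dose, which the improvement record does not. The literal text gives one answer, and the improvement record counts. The defect is that this answer is at odds with the evident purpose of the clause.

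**The sponsor's standards may already deal with it.** SAP 7.8.1 refers to three internal documents on AE analysis, display and incomplete dates. They may collapse such records. This stands: they are not available, so the finding is limited to the visible text.

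**The affected group is narrow.** This also stands. The AE must be grade 2 or higher, since grade 1 cannot step down without resolving. It must still be present after a first extension dose planned about 28 days after the last parent-trial dose. The patient must not have been excluded for a treatment-limiting AE, an uncontrolled condition or an active or severe infection (Protocol 3.3.3, criteria 2, 3 and 8). Because patients are counted, the frequency changes only if that patient has no other on-treatment event of the term, and the rate only if there is none earlier. No hypothesis is tested (Protocol 7.1), and the 5% example is a marginal case in a disclosure table, at a sample size that is only expected.

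**A corrective rule could discard real worsening.** This stands as a caution on how the rule is drafted.

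**Conclusion.** The concern holds as a minor one. On the visible text, a record created by improvement of a pre-existing AE is a primary-endpoint TEAE and ends time at risk, whereas the same AE left unchanged is not. The stated rules produce this result, so the gap is more than a missing detail.

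The bias can only be upward. Its total size cannot be derived from the documents and is probably small. The firm figure is the unit effect of 0.2 percentage points per falsely counted patient, conditional on 500 patients. The rate results and the numbers of affected patients rest on the assumptions listed above. The conclusion would fall away if the cited sponsor standards already keep such records out.

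**What to change.** In SAP 7.8.1, state that a record created solely by a decrease in intensity of an AE with onset before the first extension dose is, for analysis, a continuation of that AE. It is not counted as a TEAE and does not stop time at risk. State also that any deterioration under treatment still counts as the protocol defines it, including re-worsening after an improvement. The rule should not require intensity above that at the first extension dose. That would narrow the protocol's definition and could drop, for example, an AE that goes from grade 3 to grade 1 and back to grade 3. Because the rule departs from a literal reading of Protocol 7.2.5, note it in SAP section 4.

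If the sponsor standards already contain such a rule, one sentence citing it is enough.

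The cost is some programming and a check that links each split record to the re-recorded original. Both should be in the extension eCRF, but no linking field is visible and the protocol gives a naming rule only for increases, so the check may need manual review. No new data and no protocol amendment are needed.

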#### 5.2.6.2.2 AE reporting to the sponsor and timelines

The investigator must report SAEs, AESIs, and non-serious AEs which are relevant for the reported SAE or AESI, on the BI SAE form immediately (within 24 hours) to the sponsor's unique entry point (country specific reporting process will be provided in the ISF). The same timeline applies if follow-up information becomes available. In specific occasions, the investigator could inform the sponsor upfront via telephone. This does not replace the requirement to complete and send the BI SAE form.

With receipt of any further information to these events, a follow-up SAE form has to be provided. For follow-up information the same rules and timeline apply as for initial information. All (S)AEs, including those persisting after individual patient's end of trial must be followed up until they have resolved, have been assessed as "chronic" or "stable", or no further information can be obtained.

For further details specific to the AE reporting of this extension trial see [Section 5.2.6.2.1](#).

#### 5.2.6.2.3 Pregnancy

In rare cases, pregnancy might occur in a clinical trial. Once a patient has been enrolled in the clinical trial and has taken trial medication, the investigator must report any drug exposure during pregnancy in a trial participant immediately (within 24 hours) by means of Part A of the Pregnancy Monitoring Form to the sponsor's unique entry point.

The outcome of the pregnancy associated with the drug exposure during pregnancy must be followed up and reported to the sponsor's unique entry point on the Pregnancy Monitoring Form for Clinical Trials (Part B).

The ISF will contain the Pregnancy Monitoring Form for Clinical Trials (Part A and B).

As pregnancy itself is not to be reported as an AE, in the absence of an accompanying SAE and/or AESI, only the Pregnancy Monitoring Form for Clinical Trials and not the SAE form is to be completed. If there is an SAE and/or AESI associated with the pregnancy an SAE form must be completed in addition.

**5.4 ASSESSMENT OF BIOMARKER(S)**

#### 5.4.3 Methods of sample collection

Sampling of whole blood and serum is described in the laboratory manual in the ISF.

